6.2 On-study Evaluations and Procedures

Where multiple procedures are scheduled at the same timepoint(s) relative to dosing, the following order of events should be adhered to, where possible:

- Obtain ECGs first and then vital signs, as close as possible to scheduled times but prior to blood specimen collections.
- All other procedures should be obtained as close as possible to the scheduled time, and may be obtained before or after blood specimen collection

6.2.1 Pharmacokinetic Blood Sampling

Blood samples for PK analysis will be collected at the scheduled times via an indwelling catheter and/or direct venipuncture. Saline or heparin flushes may be used to maintain viability of indwelling catheters. Additional information may be found in the Pharmacokinetic Sample Processing Manual.

The total volume of blood required for the intensive PK profile is up to 90 mL per subject, and approximately 20 mL for all other subjects

Blood samples will be assessed for plasma concentrations of ALS-022335, ALS-022399 and ALS-022227, SMV, and ODV using validated liquid chromatography–tandem mass spectrometry methods. In addition, plasma PK samples may be stored for future analysis of the protein-binding and/or metabolite profile.

6.2.1.1 AL-335

Details on the collection, processing, storage of AL-335 PK samples are provided in the Laboratory Manual.

Blood samples will be collected to determine the concentration of ALS-022335, ALS-022399, ALS-022227 at times specified in the Schedule of Events, [Table 6-1](#) through [Table 6-4](#).

6.2.1.2 Odalasvir

Details on the collection, processing, storage of ODV PK samples are provided in the Laboratory Manual.

Blood samples will be collected to determine the concentration of ODV at times specified in the Schedule of Events, [Table 6-1](#) through [Table 6-4](#).

6.2.1.3 SMV

Details on the collection, processing, storage of SMV PK samples are provided in the Laboratory Manual.

Blood samples will be collected to determine the concentration of SMV at times specified in the Schedule of Events, [Table 6-1](#) through [Table 6-4](#).

For all samples, all efforts will be made to obtain the PK samples at the exact nominal time relative to dosing. Deviations will be defined in the study manual. The exact time of sample collection will be noted on the source document and the data collection tool.

PK samples may also be collected on an ad hoc basis as a safety assessment in the event that a safety event arises, for which an understanding of drug exposure is clinically important.

6.2.2 Laboratory Evaluations

Laboratory evaluations will be performed both locally, to enable time sensitive safety-driven decisions, and centrally, for eligibility determination (screening) and the final data analysis. The local laboratory result on Day 1 may be used to confirm continued eligibility.

The central interpretation of laboratories should also be used for clinical decision making (e.g., need for additional workup) unless the local reading is considered sufficiently concerning that it is not appropriate to delay decision making until the central reading can be performed.

In subjects that provide additional informed consent, an optional serum sample will be collected. This sample may be utilized as a back-up specimen for safety assessments. This sample may also be utilized to explore the impact patient characteristics and potential biomarkers have on treatment outcomes.

6.2.3 HCV RNA Evaluations

Blood samples for the determination of HCV RNA levels will be taken at all timepoints, processed in real time (centrally) and closely monitored by the Sponsor. The procedures for sample collection, processing and storage will be provided in the laboratory manual.

Plasma HCV RNA levels will be determined using an in vitro nucleic acid amplification test for quantification of HCV RNA in human plasma.

Results will be communicated to the Investigators throughout the study.

In case HCV RNA is detectable after previous undetectability, the results should be confirmed by an HCV RNA retest, which should be scheduled by the investigator as soon as possible (preferably within 2 weeks) after the HCV RNA results become available. This might require an unscheduled visit. At the time of the retest sample for HCV RNA, a sample for HCV resistance evaluation will also be collected.

Changes in HCV RNA levels will not be reported as AEs or SAEs.

6.2.4 HCV Resistance Evaluation

Sequencing of the HCV NS3/4A, NS5A and NS5B regions will be performed to identify pre-existing sequence polymorphisms and characterize emerging HCV viral variants. Blood samples for HCV resistance evaluation will be taken at all timepoints to identify pre-existing sequence polymorphisms and characterize the potential of emergence of viral resistance to AL-335, ODV and SMV.

The NS3/4A, NS5A and NS5B regions will be sequenced pre-treatment (from a baseline sample) by default in all subjects and post-baseline only in subjects not achieving SVR. Additional sequencing of samples may be requested upon review by the Sponsor's virologist.

Changes in viral genotype will be evaluated by the Sponsor's virologist. They will not be reported as AEs or SAEs.

Additional exploratory characterization of the viral genotype and phenotype may be performed. No human DNA analysis will be performed on these samples.

6.2.5 12-Lead Electrocardiograms

The investigator will be responsible for evaluating the results and determining if any findings are of clinical significance. Throughout the study, triplicate ECGs will be obtained in a semi-recumbent or recumbent position at the time points specified in Schedule of Events (Table 6-1 through Table 6-4). The subject should be at rest and in a (semi)recumbant position for at least 5 minutes before ECG recordings and remain resting and in that position during the recording. Triplicate ECGs will be performed 1-5 minutes apart and may be repeated at the investigator's discretion to account for erroneous readings. Sequential ECGs will be collected until 3 useful recordings are obtained without artifact.

The average of the 3 readings' ECG intervals will be used to determine if the subject meets the entry criteria or fulfills criteria which would require study drug(s) discontinuation or additional workup.

All ECG recordings must be performed using a standard high-quality, high-fidelity electrocardiograph machine equipped with computer-based interval measurements. Each ECG will be assessed by a central reader.

The centrally read screening electrocardiogram results should be used for eligibility determination. The local reading of the ECG on Day 1 may be used to confirm continued eligibility. The central interpretation of electrocardiograms should also be used for clinical decision making (e.g., need for additional workup) unless the local reading is considered sufficiently concerning that it is not appropriate to delay decision making until the central reading can be performed.

Digital ECG recording is required. A duplicate for each ECG tracing will be obtained. One copy will be sent electronically for assessment by the central reader and the other copy kept at the study center.

For safety monitoring purposes, the investigator must review, sign and date all ECG tracings. Paper copies will be kept at the study center with the subject's clinical file as part of the permanent record. The ECG intervals (HR, PR, QRS, QT, QTcB, QTcF), information on T- (normal or abnormal) and U-waves (absent/normal or abnormal), any clinically significant ECG abnormalities, and remarks will be recorded on the CRF. All ECGs will be compared over time as an assessment of safety by a central reader.

6.2.6 Echocardiograms

Echocardiograms will be performed at regular intervals (Section 6.1, Schedule of Events) and according to a standard protocol (see Study Manual). There will be a ± 3 -day visit window for these assessments except for screening visit. A variety of echocardiographic parameters, including ejection fraction and diastolic parameters will be quantitated and compared over time as an assessment of safety by a central reader.

The centrally read echocardiogram results should be used for eligibility determination. The central interpretation of echocardiograms should also be used for clinical decision making (e.g., need for additional workup) unless the local reading is considered sufficiently concerning that it is not appropriate to delay decision making until the central reading can be performed.

6.2.7 Vital Signs

Vital signs (oral or body temperature, RR, automated supine BP and HR) will be obtained in a semi-recumbent or recumbent position after 5 minutes of rest. Blood draws will take precedence over vital signs in the event that the 2 procedures need to be conducted at the same time. In this case, vital signs should be obtained as close to the scheduled time as possible, after ECG assessments and prior to blood collections.

6.2.8 Physical Examinations

Complete Physical Exams, including vital signs (BP, HR, RR, body temperature), are to be done at screening, predose on Day 1, early termination, safety follow-up visits. A brief symptom directed examination will be conducted at all other timepoints as indicated in the Schedule of Events. BMI will be calculated by clinic staff at the Screening visit using the following formula:

$$\text{BMI} = \text{weight in kg} \div (\text{height in meters})^2$$

6.2.9 Contraception

Contraception requirements from screening through completion of the study are defined in the Inclusion criteria (see Sections 4.2 and 4.3).

7.0 SAFETY MONITORING AND REPORTING

7.1 Definitions

7.1.1 Pretreatment Events

A pretreatment event is any event that meets the criteria for an AE/SAE and occurs after the subject signs the ICF but before receiving the first administration of study drug.

7.1.2 Adverse Events

An AE is any event, side effect, or untoward medical occurrence in a subject enrolled in a clinical trial whether or not it is considered to have a causal relationship to the study drug. An AE can therefore be any unfavorable and unintended sign, symptom, laboratory finding outside of normal range with associated clinical symptoms or suspected latent clinical symptoms in the opinion of the investigator, physical examination finding, or disease temporally associated with

the use of the study drug, whether or not the event is considered related to the study drug. This includes any occurrence that is new in onset or aggravated in severity or frequency from the baseline condition, or abnormal results of diagnostic procedures, including laboratory test abnormalities.

Note: The sponsor collects AEs starting with the signing of the ICF.

Planned hospital admissions or surgical procedures for an illness or disease that existed before the subject was enrolled in the study are not to be considered AEs unless the condition deteriorated in an unexpected manner during the study (e.g., surgery was performed earlier than planned).

7.1.3 Serious Adverse Events

An SAE is any untoward medical occurrence at any dose that:

- Results in death: This includes deaths that appear to be completely unrelated to study medication (e.g., a car accident).
- Is a life-threatening event: An event that places the subject at immediate risk of death at the time of the event; it does not refer to an event that hypothetically might have caused death if it were more severe.
- Requires inpatient hospitalization or prolonged hospitalization of an existing hospitalization.
- Results in permanent or prolonged (at least 28 days in duration) disability or incapacity.
- Is a congenital anomaly or birth defect in the offspring of a study subject.
- Medically important event: An event that may not be immediately life-threatening, or result in death or hospitalization, or require intervention to prevent one of the outcomes listed above, but is considered medically significant for other reasons. An opportunistic or otherwise unusual infection for the investigator's practice, such as tuberculosis, will be considered medically significant.

The term severe is used to describe the intensity of a specific event (as in mild, moderate, or severe); the event itself, however, may be of minor medical significance (such as severe headache). This is not the same as serious, which is based on outcome of the event, as described above. Seriousness, not intensity, serves as a guide for defining regulatory reporting obligations.

7.2 Documenting and Reporting of AEs (including SAEs)

Adverse events will be evaluated and documented using the grading scales contained in the Division of AIDS Table for Grading the Severity of Adult and Pediatric Adverse Events (November 2014) and shown in [Appendix F](#).

7.2.1 Documenting and Reporting Pretreatment Events

For enrolled subjects, record all pretreatment AEs that occur after the subject signs the ICF but before the first study drug administration on the AE CRF and Clinical Trials SAE Form (if applicable). The AE CRF and SAE form will indicate that the event occurred prior to the first dose of study drug.

7.2.2 Documenting and Reporting AEs

Record all AEs that occur from Day 1 (from start of study medication administration) to the follow-up visit, regardless of the intensity, seriousness, or relationship to study drug, on the AE CRF, for all enrolled subject. Subjects who do not enroll (i.e., screen failures), collect AEs until the time of screen failure.

Once an event has resolved, any recurrence will be reported as a new event with a corresponding grade.

Clinically significant changes in objective findings (e.g., laboratory, ECG, physical examination) should be considered AEs only if they meet the following criteria:

- Associated with accompanying symptoms; and/or,
- Require medical/surgical intervention; and/or,
- Lead to discontinuation from the study; and/or
- Lead to significant additional concomitant drug treatment, or other therapy; and/or,
- Lead to any of the outcomes included in the definition of an SAE.

Whenever possible, the etiology of the abnormal findings (rather than the abnormal finding(s) itself) should be documented as the AE. Repeated additional tests and/or other evaluations required to establish the significance and etiology of an abnormal result should be obtained when clinically indicated. An AE includes the following:

- Pre-existing event that increases in frequency or intensity.
- Condition detected or diagnosed during the study period, even though it may have been present, in retrospect, prior to the first dose of study drug.
- Laboratory abnormalities outside of normal limits and requiring therapeutic intervention.
- An overdose of the study drug without any signs or symptoms will be considered an AE. A calculated dose that exceeds its correct dose by 10% or more and is administered to the subject will be considered an overdose and documented as an AE.

The following events **will not** be identified as AEs in this study:

- Progression or exacerbation of the subject's underlying disease. However, clinical sequelae that result from disease progression, such as pleural effusion or small bowel obstruction, are reportable as AEs.
- Medical or surgical procedures (e.g., surgery, endoscopy, tooth extraction, etc); however, the condition (the "triggering event") that leads to the procedure may be an AE.
- Pre-existing conditions present or detected prior to the first dose of study drug that do not worsen.

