4.6.1 Subject Treatment Discontinuation Criteria

If a subject's study drug treatment must be discontinued before the end of the treatment regimen, this will not result in automatic withdrawal of the subject from the study.

A subject's study drug treatment (AL-335, SMV and ODV) must be permanently discontinued if:

- The investigator believes that for safety reasons (e.g., AE), it is in the best interest of the subject to discontinue study drug treatment.
- The subject becomes pregnant.
- The subject has evidence of muscle injury (Section 7.5.1) or cardiac toxicity (Section 7.5.2 and 7.5.3).
- The subject has a Grade 4 rash; see Section 7.6.
- The subject has a Grade 3 or 4 allergic reaction; see Section 7.7.
- The subject has a confirmed Grade 4 ALT and/or AST value that is $>2\times$ the baseline value; see Section 7.9.
- The subject has a confirmed Grade 4 bilirubin value which is considered a sign of worsening liver disease, or for which there is no identifiable explanation; see Sections 7.8 and 7.9.
- The subject has severe worsening of hepatic disease.
- The subject has a confirmed diagnosis of pancreatitis.
- The subject has a Grade 4 AE or laboratory abnormality at least possibly related to 1 of the study drugs and which is considered clinically significant (laboratory abnormalities only).
- The subject requires treatment with any of the medications reported on the list of disallowed medications; see Section 5.12.
- The subject experiences inadequate virologic response or viral breakthrough (refer to Definitions)
- An event occurs which triggers the study treatment stopping criteria (Section 4.7.1)

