7.5.2 Cardiotoxicity

A theoretical risk of nucleosides is mitochondrial toxicity that can manifest as cardiac toxicity/congestive heart failure. Surveillance for this theoretical risk will be done in this study via assessments of AEs, ECGs and echocardiograms, which will be obtained at specified timepoints during the treatment period in this study.

In order to effectively monitor for potential treatment-related cardiotoxicity during the study, subjects presenting at screening must have:

- ECG PR interval must be < 200 msec and there must be no evidence of any conduction blocks.
- echocardiogram ejection fraction (EF) must be $\geq 55\%$.

During the treatment period, emergence of or changes in symptoms or clinically significant findings in ECG may trigger the following stopping criteria:

If a first degree AV block is diagnosed and:

- The PR interval is > 200 msec but ≤ 240 msec, study drugs can be continued. Close monitoring with weekly ECG is recommended.
- The PR interval is > 240 msec but ≤ 300 msec (confirmed by a repeat triplicate analysis at least 30 minutes after the initial assessment), an assessment of the subject's clinical status, including symptoms, physical examination and other clinical parameters should be made. Based on this assessment, the study drugs may or may not be continued. Close monitoring with weekly ECG is recommended.

- The PR interval is >300 msec (confirmed by a repeat triplicate analysis at least 30 minutes after the initial assessment, irrespective of presence or absence of clinical symptoms), ODV must be discontinued. The Investigator and Sponsor Medical Monitor must determine whether or not continued dosing with AL-335 and SMV is acceptable for subjects that discontinue ODV.
- If a second degree or higher AV block is diagnosed (confirmed by a repeat triplicate analysis at least 30 minutes after the initial assessment and irrespective of presence or absence of clinical symptoms), ODV must be discontinued. The Investigator and Sponsor Medical Monitor must determine whether or not continued dosing with AL-335 and SMV is acceptable for subjects that discontinue ODV.

All study medications must be discontinued:

- In asymptomatic patients with no clinical evidence of congestive heart failure:
 - If the absolute decline from baseline in EF is >10% AND the post-baseline EF is <50%; e.g., 60% →49%)

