### 8.1 Adverse events

Adverse events, including pre-treatment events, will be recorded from the time of consent through the completion visits, for the treatment and follow-up phase combined.

Adverse events will be coded according to MedDRA® Version 19.1.

A treatment-emergent adverse event (TEAE) is an adverse event that occurs after the first IMP administration or that was present prior to dosing but exacerbated after the first IMP administration.

Adverse events will be summarised in tables as follows (overall and by System Organ Class (SOC) and Preferred Term (PT)):

- Number and percentage of subjects with at least one adverse event and number of adverse events for each cohort,
- Number and percentage of subjects with at least one TEAE and number of TEAEs for each cohort,
- By intensity, with the number and percentage of subjects with at least one TEAE and number of TEAEs for each cohort,
- By causality of each treatment, with the number and percentage of subjects with at least one TEAE and number of TEAEs for each cohort.

Moreover, an overall summary table of all TEAEs will be presented.

In addition, summary tables will also be presented for TEAEs, serious TEAEs, TEAEs leading to any study drug discontinuation, severe or life threatening (i.e. Grade 3 / 4) TEAEs, and TEAEs with fatal outcome by decreasing frequency of PT.

The incidence and comparable prevalence rate per 2-week time interval for any AEs will be summarized and plotted by cohort.

Note: Repetitions will only be counted once in summary tables. Repetitions are defined as follows: if a given subject presents several adverse events with the same preferred term during the same phase (treatment and follow-up phase combined), only one event is counted, the others are considered repetitions or recurring episodes. The start time of the event will be the start time of the first occurrence, the end time will be the end time of the last episode. The intensity will be the highest recorded intensity for all episodes. The causality will be the highest likelihood recorded for all episodes.

A summary table of TEAEs of special interest (cardiac events, increased bilirubin (hyperbilirubinemia, blood bilirubin increased), rash and photosensitivity) will be also presented (see Appendix 4 for detailed list of SMQs).

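### The AE recording rule covers findings that take a subject out of the study but not findings that stop study drug, so sites may record the same event differently and AE-derived tables may be incomplete

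*Protocol*

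**What the plan says.** Protocol 7.2.2 sets the operational rule: "Clinically significant changes in objective findings (e.g., laboratory, ECG, physical examination) should be considered AEs only if they meet the following criteria". There are five criteria: accompanying symptoms, a need for medical or surgical intervention, significant added treatment, an outcome that would make the event serious, and "Lead to discontinuation from the study; and/or". Interrupting or stopping study drug is not among them.

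Protocol 4.6.1 says of early treatment discontinuation that "this will not result in automatic withdrawal of the subject from the study". Section 4.6.2 then follows these subjects off treatment for up to 24 weeks, or until other therapy begins. Section 4.6.3 limits withdrawal from the study to loss to follow-up, withdrawn consent and death.

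Protocol 7.5.2 covers PR above 300 msec and AV block of second degree or higher: "irrespective of presence or absence of clinical symptoms), ODV must be discontinued".

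Protocol 7.1.2 gives a wider AE definition, which takes in new or worsened occurrences "or abnormal results of diagnostic procedures, including laboratory test abnormalities".

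The same section 7.2.2 excludes progression or exacerbation of the underlying disease but keeps reportable the "clinical sequelae that result from disease progression, such as pleural effusion or small bowel obstruction". Among the mandatory drug stops in 4.6.1 is: "The subject has severe worsening of hepatic disease".

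SAP 8.1 plans a summary of "TEAEs leading to any study drug discontinuation", with tables of Grade 3/4 TEAEs, TEAEs of special interest and time to first event of interest.

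**The concern.** The surveillance programme is designed to catch silent conduction, cardiac-function, muscle, renal and liver findings and to act on them by stopping drug. Read literally, 7.2.2 does not make such a finding an AE when the only consequence is a drug stop, because the subject remains in the study. A site that follows 7.1.2 would record it; a site that follows 7.2.2 might not.

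AE tabulation is the first component of the primary endpoint (Protocol 3.2.1). The SAP's discontinuation, severity, special-interest and Kaplan-Meier outputs all start from AE records. Its special-interest terms (SAP Appendix 4) include PR prolongation, first-degree AV block, decreased ejection fraction and increased bilirubin, all of which can be silent. Study cohorts have 10 to 20 subjects and there is no comparator arm, so uneven recording would be hard to detect from the AE tables alone.

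**Working it through.** This is mainly a check of text against text.

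**1. Does a drug stop satisfy any 7.2.2 criterion?** Take a finding that causes no symptoms, needs no added therapy and has no serious outcome.

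| Finding | Action on study drug | Where | Symptoms needed? |
|---|---|---|---|
| PR >300 msec, or AV block of second degree or higher | ODV stopped | 7.5.2 | No |
| EF decline >10% to below 50% | All drugs stopped | 7.5.2 | No |
| CK ≥20×ULN on repeat, no other likely cause | Drug stopped | 7.5.1 | No |
| eGFR <30 confirmed | All drugs interrupted | 7.5.4 | No |
| Grade 4 ALT/AST >2× baseline, confirmed | All drugs stopped | 4.6.1, 7.9 | No |
| Grade 4 bilirubin confirmed, judged worsening liver disease or unexplained | All drugs stopped | 4.6.1, 7.9 | No |

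In each row the subject stays in the study under 4.6.1 to 4.6.3, so the leaving-the-study criterion is not met. The intervention criterion does not clearly help. Section 7.2.4 treats stopping drug as an action taken in response to an AE, and the Appendix F glossary defines intervention as treatment of an AE. Both presuppose that an AE already exists. Section 4.6.1 also lists a Grade 4 AE and a Grade 4 laboratory abnormality as alternatives, so the protocol itself foresees a laboratory finding that stops drug without being an AE.

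**2. Does another section close the gap?** Section 4.6.4 sends an abnormal laboratory value to the AE form, but it is worded for discontinuation from the study and does not name ECG or echocardiogram. Section 7.1.2 is wide enough but conflicts with the restrictive wording of 7.2.2.

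**3. Which outputs are affected?** Those built on AE records: the SAP 8.1 tables named above, and the PK listings in SAP 7.2.2 for subjects who discontinue for an AE or have a severe or serious one. Not affected: graded laboratory values (SAP 8.2), PR categories including >300 ms (SAP 8.3.2) and EF declines (SAP 8.3.3).

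**4. The one planning figure that relies on AE recording.** Protocol 9.3 gives the chance of seeing at least one AE among 320 subjects. The formula is 1 − (1 − p)^320.

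- p = 1%: 1 − 0.99^320 = 95.99% (stated 96%)
- p = 0.8%: 92.35% (stated 92%)
- p = 0.5%: 79.9% (stated 80%)
- p = 0.1%: 27.4% (stated 27%)

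All four reproduce, and all assume that every event is recorded. Suppose instead that a fraction f of a 1%-incidence drug-stopping finding reaches the AE form. The formula becomes 1 − (1 − 0.01f)^320:

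- f = 75%: 91%
- f = 50%: 80%
- f = 25%: 55%

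The values of f are assumptions. The documents give no recording rate.

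**The case against.** The best defence is that the protocol offers several routes to an AE record.

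- **Diagnosed conditions.** Section 7.2.2 goes on to count conditions detected or diagnosed on study, and 7.5.2 frames the ECG stops as diagnoses of AV block. This has some force for AV block. It has less for an isolated EF, CK, eGFR or ALT value, and the same list ties laboratory abnormalities to a need for therapeutic intervention.
- **Medically important events.** An investigator may call a silent finding serious under 7.1.3. That is a judgement, not a recording rule.
- **Intended meaning.** Since 4.6.3 allows withdrawal from the study only for loss to follow-up, consent or death, the 7.2.2 criterion would do almost no work unless its authors meant treatment discontinuation. Section 4.6 also mixes the two uses. This is a fair guess at intent, and 4.6.4 would then cover laboratory stops. It supports correcting the wording rather than leaving it.

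Three stronger inferences are not supported.

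- A reader might infer that the findings drop out of the primary endpoint. They do not: ECG, echocardiogram and laboratory results are named in Protocol 3.2.1 and tabulated whatever their AE status. SAP 6.5 also lists dosing dates for each drug.
- A reader might infer that worsening liver disease goes unreported. The exclusion concerns the underlying disease and keeps clinical sequelae reportable, so overt decompensation would be captured. What remains unclear is non-clinical worsening that stops drug. The examples given, pleural effusion and bowel obstruction, offer little guidance for hepatitis C.
- A reader might project a count, for instance 1% to 3% of 320 (3.2 to 9.6 subjects) missing from the discontinuation table, or most of that table. No such rate is given, and the projection assumes that every such stop goes unrecorded. The Wenckebach case in this study (1/123 = 0.8%) is not shown to be an unrecorded drug stop. The one in an earlier eight-subject study completed 12 weeks of therapy. PR above 200 msec in 4 of 32 volunteers is below the level at which 7.5.2 requires a stop.

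**Conclusion.** The gap is real. Followed as written, 7.2.2 allows a silent finding that stops or interrupts study drug to go unrecorded as an AE, while 7.1.2 points the other way. The result is inconsistent recording and possible omissions from AE-derived outputs: TEAEs leading to drug discontinuation, Grade 3/4 TEAEs, cardiac and bilirubin events of special interest, and time to first event.

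The size cannot be stated from the documents. The conclusion rests on sites applying the 7.2.2 list literally and on the finding having no symptoms, added treatment or serious outcome. It matters most for the discontinuation table, which may hold few events, so that two or three omissions could change how it reads.

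**What to change.** 1. In Protocol 7.2.2, widen the discontinuation criterion to cover interruption or permanent stopping of any study drug as well as leaving the study.
2. Align 4.6.4 with it, covering treatment discontinuation and naming ECG and echocardiogram findings, and reconcile 7.1.2 with 7.2.2.
3. State that hepatic worsening that triggers a drug stop under 4.6.1 is recorded as an AE despite the underlying-disease exclusion.
4. Before database lock, list every subject whose drug was stopped or interrupted under 4.6.1, 7.5 or 7.9 and query the AE form for each. The dosing listing in SAP 6.5 is a natural starting point.

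The cost is a few wording changes and a short data query. AE and discontinuation counts may rise slightly. The change concerns recording only and alters no clinical stopping rule.
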